**Figure 11-1 Analysis Cycle Illustration**

Treatment	Cycles for Safety Data Analyses	
	SLT eye	BIM SR eye
SLT	Analysis Cycle 1	Analysis Cycle 1
Bim SR 1st implant	Analysis Cycle 1	Analysis Cycle 1
Bim SR 2nd implant	Analysis Cycle 2	Analysis Cycle 2
Bim SR 3rd implant	Analysis Cycle 3	Analysis Cycle 3

## 11.1 ADVERSE EVENTS

Adverse events will be coded by system organ class and preferred term using the Medical Dictionary for Regulatory Activities, version 21.0 or newer. An AE with the same PT may have two different worst severities associated with two eyes separately or could be associated with only one eye. For summary by severity of each PT, the highest severity will be counted for each eye separately. Therefore, the comparison of AE incidence rates will be conducted at the same treatment exposure across Bim SR eye and SLT eye.

An AE will be considered a treatment-emergent adverse event (TEAE) for the study treatment period if the AE meets one of the following criteria:

- The onset date is on or after the first study treatment date.
- The onset date is before the first study treatment date and either:
  - The severity of the event worsened on or after the first treatment date.
  - The event became serious on or after the first study treatment date.

An AE will be considered as a TEAE for a treatment cycle if the AE meets one of the following criteria:

- The onset date is on or after the treatment administration of the cycle but prior to the next cycle administration.
- The onset date is before the treatment administration of the cycle and either:
  - The severity of the event worsened on or after the treatment administration of the cycle.
  - The event became serious on or after the treatment administration of the cycle.

An ocular AE will be defined by the location information on the adverse event page in eCRF. Additionally, questions about adverse event relationships to study treatment and study procedure will be asked in eCRF, and the answers to these questions will be used together to derive the treatment related TEAE.

An overall summary of patient incidences of TEAEs will be presented by event type and event category (ocular or non-ocular). These summaries will include the following:

- All TEAE
- Treatment-related TEAE
- TEAE related to study procedure:
  - Related to study drug
  - Related to study drug administration procedure
  - Related to SLT laser
- All serious TEAE
- Treatment-related serious TEAE

- Serious TEAE related to study procedure:
  - Related to study drug
  - Related to study drug administration procedure
  - Related to SLT laser
- Any TEAE leading to Bim SR implant removal
- Any TEAE leading to study discontinuation

The following non-ocular adverse events will be summarized by SOC and PT:

- Any non-ocular TEAEs,
- Any treatment related non-ocular TEAEs,
- Any serious non-ocular TEAEs, and
- Any non-ocular TEAEs leading to study discontinuation.

Additionally, a summary by SOC, PT, and severity will be provided for non-ocular TEAEs.

For patient eye incidences of treatment emergent ocular adverse events, overall and by period summaries will be provided for the following categories:

- Any ocular TEAEs by SOC and PT
- Any ocular TEAEs by SOC, PT, and severity
- Any treatment related ocular TEAEs by SOC and PT
- Any serious ocular TEAEs by SOC and PT
- Any ocular TEAEs leading to study discontinuation by SOC and PT
- Any ocular TEAEs within two days of study treatment by SOC and PT
  - i.e, Ocular TEAEs that occur within two days from the Bim SR treatment or Bim SR sham
- Any ocular TEAEs after two days of study treatment by SOC and PT
  - i.e, Ocular TEAEs that occur after two days from the Bim SR treatment or Bim SR sham to next Bim SR treatment or Bim SR sham
- SLT procedure related ocular TEAEs by SOC and PT
  - i.e, Ocular TEAEs that occur starting from Day 1, but before the first Bim SR treatment will be summarized.

- Any corneal TEAEs of interest by SOC and PT (Corneal AEs of interest will be identified separately prior to database lock.)
- Any anterior segment inflammation TEAEs of interest by SOC and PT (Anterior segment inflammation AEs will be identified separately prior to database lock.)

## 11.2 VITAL SIGNS

Vital signs (systolic and diastolic blood pressures [mmHg], pulse rate [bpm], and temperature [Celsius]) will be collected at baseline, but will not be analyzed.

## 11.3 OTHER SAFETY PARAMETERS

Blood and urine samples obtained for the analysis of blood chemistry, hematology, and urinalysis will be reviewed by the investigator or qualified site personnel for any adverse events. Any safety laboratory test results that represent adverse events will be reflected on adverse event eCRF page, and thus will be part of the suggested analyses of AEs. Therefore, laboratory data collected will not be analyzed.

### 11.3.1 Pregnancy

Pregnancy test results for female patients of childbearing potential will be collected, but will not be analyzed or listed.

### 11.3.2 Best Corrected Visual Acuity

Best-corrected visual acuity (BCVA) at an assessment timepoint is recorded in Snellen equivalent units on eCRF as 20/8, 20/10, 20/12.5, 20/16, ..., or 20/800. An increase in the second number (denominator) in Snellen equivalent unit indicates worsening of VA and a decrease indicates an improvement. For example, change from 20/32 to 20/40 is a worsening of VA by one line, 20/32 to 20/20 (note that 20/25 is in between) is an improvement by 2 lines.

The line change from baseline at each post-baseline evaluation can be calculated using the formula:

$$\text{Line change} = 10 \times [\log_{10}(d_{BL}/d_{PBL})]$$

where  $d_{BL}$  = denominator of the Snellen equivalent unit at baseline,  
 $d_{PBL}$  = denominator of the Snellen equivalent unit at post-baseline

The logarithmic value in the formula above needs to be rounded to the nearest tenth before proceeding to the calculation of the line change. A positive value indicates an

improvement, a negative value indicates a worsening, and a zero indicates no change. For example, the line change for a Snellen equivalent unit at baseline of 20/25 followed by a Snellen equivalent unit of 20/80 at a post-baseline visit would be:

$$\text{Line change} = 10 \times [\log_{10}(25/80)] = 10 \times (-0.5) \text{ (rounded to nearest tenth)} = -5$$

representing a worsening of 5 lines in VA. Note that there are 4 Snellen equivalent units (20/32, 20/40, 20/50 and 20/63) between 20/25 and 20/80, thus moving from 20/25 to 20/80 is a worsening by 5 lines in VA because the denominator has increased.

The greatest line change in best corrected visual acuity (BCVA) from baseline will be summarized for each eye with respect to number of line change categories by study period. Categories will be summarized as worsening VA of 2 lines or more, worsening of one line, no change, improvement of one line, and improvement of 2 lines or more.

### 11.3.3 Visual Field

Visual field examinations will be assessed by automated perimetry with either Humphrey Field Analyzer (using 24-2 full threshold or 24-2 [SITA] Standard program) or Octopus Perimeter (using G1 Dynamic or Normal strategy or 24-2 Dynamic or Normal strategy program) at Screening, Baseline, Week 24, and Week 52/Exit by test methods. The same test methodology should be used throughout the entire study for a given patient. Visual field overall results will be recorded on the eCRF as normal or abnormal. Abnormal findings include enlargement of blind spot, superior arcuate scotoma, inferior arcuate scotoma, paracentral scotoma, nasal step, central scotoma, generalized depression, and temporal scotoma and other. An eye may exhibit multiple abnormalities. In addition, mean deviation or mean defect (MD) and change from baseline will also be recorded in decibels (dB), and will be analyzed by visit and by machine type (Humphrey and Octopus respectively). If the machine type is different between baseline and post baseline visit, no change from baseline will be derived and machine type will not be imputed. For patients whose visual fields were assessed by one machine type as recorded, the mean deviation or mean defect assessments with missing machine type will be imputed as assessments by the corresponding unique machine type.

Any post-baseline abnormal findings on visual field will be summarized by eye using number and percentage format to calculate patient incidences overall and by analysis cycle.

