1.1 Glaucoma and Treatment

Glaucoma is a family of diseases commonly characterized by progressive optic neuropathy with associated visual field defects and is the leading cause of irreversible blindness in the world. Glaucoma is classified by Becker-Shaffer into 3 broad types: developmental, angle-closure, and open-angle glaucoma (OAG) (Stamper et al, 2009). Open-angle glaucoma is further categorized into primary OAG (POAG, sometimes also referred to as chronic OAG) and secondary OAG (which includes pigmentary and pseudoexfoliation glaucoma), the former being the predominant form of OAG. Primary OAG is characterized as a multifactorial optic neuropathy with a characteristic acquired atrophy of the optic nerve and loss of ganglion cells and their axons, developing in the presence of open anterior chamber (AC) angles, and manifesting characteristic visual field abnormalities (American Academy of Ophthalmology, 2010a). Globally, over 60 million people are estimated to be affected by glaucoma (the majority of whom have OAG) and these numbers are expected to increase over time (Quigley and Broman, 2006; Varma et al, 2011; Cook and Foster, 2012). Approximately 10% of eyes with elevated intraocular pressure (IOP) will progress to OAG over the course of a decade (Quigley et al, 1994).

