## 11.0 SAFETY ANALYSES

All safety analyses will be performed using the Safety Population. As indicated in [Section 6.5](#), safety data collected at Screening for eligibility assessment will not be analyzed.

Non-ocular safety assessments include: non-ocular adverse events (AEs), clinical laboratory, vital signs (blood pressure, pulse rate and temperature), and pregnancy test. Ocular safety will be evaluated through: ocular AEs, best corrected visual acuity, visual field examination, specular microscopy, macroscopic iris color assessment, macroscopic conjunctival hyperemia assessment, gonioscopy / angle assessment, biomicroscopy (using a slit lamp), lens assessment, optic disc examination, dilated ophthalmoscopy, pachymetry, and anterior segment-optical coherence tomography.

[REDACTED]

Unless otherwise stated, the last non-missing safety assessment before the SLT treatment (Day 1) will be used as the baseline for all analyses of that safety parameter.

Analysis study periods are defined as follows:

- **During the study:** Date of SLT treatment through Week 52/Exit visit/last study visit available.
- **Analysis Cycle 1:** SLT Treatment date (Day 1) through the second Bim SR implant date – 1. If the second Bim SR implant was not given to a patient, all safety assessments through Week52/Exit visit/last study visit available will be included in analysis cycle1.
- **Analysis Cycle 2:** Second Bim SR implant date through the third Bim SR implant date – 1. If the third Bim SR implant was not given to a patient, all safety assessments through Week52/Exit visit/last study visit available will be included in analysis cycle 2.
- **Analysis Cycle 3:** Third Bim SR implant date through Week 52/Exit visit/last study visit available. Note that only Stage 1 patients were eligible to receive third Bim SR implant.

All summaries will be based on the first treatment received in each eye (Bim SR or SLT), except one patient who received both SLT and Bim SR in the same eye (Safety assessment will be summarized in Bim SR). For non-ocular safety measures, overall summaries will be presented. For ocular safety assessments, summaries will be presented for the periods of during the study, Analysis Cycle 1, Analysis Cycle 2, and Analysis Cycle 3 as shown in Figure 11-1 below.

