### 11.3.7 Biomicroscopy and Dilated Ophthalmoscopy

Biomicroscopy will be performed in each eye by slit-lamp examination at Screening, Baseline, and during Cycle 1, Cycle 2, Follow-up, and during Cycle 3 for Stage 1 patients.

At these exams, any findings noted on the following will be recorded for each eye on the eCRF as follows:

- Eyelids/Eyelid Margins/Lashes
  - Erythema
  - Edema
  - Other
- Conjunctiva (Bulbar or Palpebral)
  - Hyperemia
  - Edema
  - Subconjunctival Hemorrhage
  - Pterygium, encroaching on visual axis
  - Pterygium, not encroaching on visual axis
  - Other
- Cornea
  - Punctate Epithelial Staining
  - Infiltrates
  - Edema
  - Corneal Guttata
  - Endothelial Pigment

- Keratic Precipitates
- Neovascularization
- Opacity(ies)
- Stromal Haze
- Other
- Anterior Chamber
  - Cells
  - Flare
  - Hypopyon
  - Hyphema
  - Other
- Iris/Pupil
  - Afferent Pupillary Defect (APD)
  - Posterior Synechiae
  - Transillumination Defect(s)
  - Pseudoexfoliative Material
  - Peripheral Iridectomy
  - Laser Peripheral Iridotomy
  - Other

Severity of findings in the categories of Eyelids/Eyelid Margins/Lashes, Conjunctiva (Bulbar or Palpebral) and Cornea will be recorded as +0.5 (Trace), +1 (Mild), +2 (Moderate), +3 (Severe) or Not Applicable. Severity of Anterior Chamber findings will be recorded as +0.5, +1, +2, +3, +4, or Not Applicable using the Standardization of the Uveitis Nomenclature (SUN) Working Group criteria. No severity grade will be assigned for Iris/Pupil findings, and only findings noted will be recorded.

Biomicroscopy findings will be coded using MedDRA. Number and percentage of patient eyes with findings showing more than one grade increase from baseline will be presented by coded PT (more than 1 severity grade increase means a change from 0 to 2 and above, from 0.5 to 2 and above, or from 1 to 3 and above from baseline at any of the follow-up visits). Number and percentage of patient eyes with findings present at post-baseline which did not present at baseline will be summarized (i.e., findings not associated with a severity grade). The analysis results will be presented by study periods and analysis cycle.

Dilated ophthalmoscopy and lens status and opacity assessments will be performed in each eye at Screening, Baseline, Week 12, Week 24, Week 40, and Week 52/Exit. At ophthalmoscopy exams, any findings noted on the following areas will be recorded for each eye:

- Vitreous (each finding will be entered as free text field)

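### The visual-field safety table counts defects present before treatment as incidence, and its split by analysis cycle does not fit the visual-field schedule

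*SAP*

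**What the plan says.** SAP 11.3.3 has fields assessed "at Screening, Baseline, Week 24, and Week 52/Exit by test methods". Each eye is recorded as normal or abnormal. Abnormal fields are classified into eight named finding types plus an other category, and one eye may have several. Two summaries follow:

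- Mean deviation or mean defect, with change from baseline, by visit and by machine type.
- A categorical table: "Any post-baseline abnormal findings on visual field will be summarized by eye using number and percentage format to calculate patient incidences overall". The sentence runs on so that the output is "patient incidences overall and by analysis cycle".

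SAP 11.0 defines Analysis Cycle 1 as "SLT Treatment date (Day 1) through the second Bim SR implant date" minus one day, and adds: "If the second Bim SR implant was not given to a patient, all safety assessments through Week52/Exit visit/last study visit available will be included" in that cycle. It also sets baseline for safety parameters as the most recent non-missing value before SLT, unless stated otherwise.

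For slit-lamp findings without a severity grade, SAP 11.3.7 applies a different rule: eyes with "findings present at post-baseline which did not present at baseline will be summarized". Graded findings there need an increase of more than one grade, and ophthalmoscopy is handled similarly.

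**The concern.** The categorical table is labelled incidence, but its rule describes prevalence after treatment. That matters in this population. Protocol 4.3 (criterion 10) admits eyes with open-angle glaucoma or ocular hypertension, and Protocol 1.1 describes primary open-angle glaucoma as "manifesting characteristic visual field abnormalities". Protocol 4.4 (criterion 27) excludes field loss only if it is functionally significant in the investigator's opinion or shows progression in the preceding year. A stable, non-threatening nasal step or arcuate defect can therefore be present at entry and recorded again at Week 24 and Week 52.

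A reader who takes the percentages as new loss on treatment would be misled about its level, and a real difference between Bim SR and SLT eyes would look proportionally smaller than it is.

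A reader who sets the Cycle 1 percentage beside the Cycle 2 percentage would be comparing largely different patients. A change between the columns could then be mistaken for an effect of repeat dosing.

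**Working it through.** The plan gives no figure to reproduce here. The check has two parts.

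**1. Timing of fields against the cycle boundary**

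Inputs: second implant at Week 16, window -2/+4 days (Protocol 8.4.3.7); post-treatment fields at Week 24 ±4 days and Week 52/Exit ±7 days (Protocol Tables 4 and 6; SAP Tables 4-4 and 4-6). SAP Table 4-3 has no visual-field row. With SLT as day 1, the target day is 7 × week + 1.

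- Second implant: 7 × 16 + 1 = 113, window 111 to 117.
- Week 24 field: 7 × 24 + 1 = 169, window 165 to 173.
- Week 52 field: 7 × 52 + 1 = 365, window 358 to 372.
- Smallest in-window gap from implant 2 to the Week 24 field: 165 − 117 = 48 days. Counting all visits from the first implant on Day 4 shifts every window by 3 days and leaves the gap at 48.

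| Patient group | Scheduled fields in Cycle 1 | Cycle 2 | Cycle 3 |
|---|---|---|---|
| No second implant | Week 24, Week 52/Exit | none | none |
| Two implants | none | Week 24, Week 52/Exit | none |
| Three implants (Stage 1) | none | Week 24 | Week 52/Exit |

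Scheduled fields in the Cycle 1 column thus come only from patients without a second implant. These include patients stopped by Amendment 3, patients whose Bim SR eye received nonstudy IOP-lowering treatment before Week 16 (Protocol 4.5.2 substitutes sham), and patients who left early. SAP 11.3.3 gives no denominator rule. If all treated eyes were used, eyes without a field in Cycle 1 would count as having no finding, and the percentage would be too low.

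**2. Size of the dilution (illustration only)**

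Let p be the share of eyes abnormal at baseline and i the true new-defect rate among eyes normal at baseline. If pre-existing defects persist and all findings are collapsed to one abnormal/normal row, the displayed rate is p + (1 − p) × i. For example, p = 0.30 gives 0.30 + 0.70 × 0.05 = 33.5% and 0.30 + 0.70 × 0.10 = 37.0%. Neither p nor i is in the documents, so the table uses assumed ranges.

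| p | Displayed, i = 5% vs 10% (true ratio 2.0) | Ratio | Displayed, i = 2% vs 6% (true ratio 3.0) | Ratio |
|---|---|---|---|---|
| 10% | 14.5% vs 19.0% | 1.31 | 11.8% vs 15.4% | 1.31 |
| 30% | 33.5% vs 37.0% | 1.10 | 31.4% vs 34.2% | 1.09 |
| 50% | 52.5% vs 55.0% | 1.05 | 51.0% vs 53.0% | 1.04 |
| 70% | 71.5% vs 73.0% | 1.02 | 70.6% vs 71.8% | 1.02 |

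The 10% row also indicates the effect if results are shown by finding type, where the baseline share per row would be smaller. Dilution is then milder but still present.

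**The case against.** The strongest case on the other side is that little depends on this table. Mean deviation change from baseline is analysed by visit, which is a baseline-adjusted measure at the visits that matter. SAP 16.4 puts all assessments in the listings, so pre- and post-treatment findings can be compared eye by eye. The table specifications are in a separate document (SAP 4.0) and may add a baseline column, rows by finding or a sensible denominator. The cycle split is the general convention of SAP 11.0 for ocular safety, and no formal comparison of cycles is planned.

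Much of this stands, and it limits the consequence. It does not remove the defect: the SAP text sets no baseline condition, and a mean change in decibels can miss a new focal defect in a few eyes.

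Three stronger readings are tempting, and the documents do not support them.

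- *That the table mainly measures disease at entry.* Baseline prevalence is not reported, ocular hypertension eyes are eligible, and the Protocol 1.1 description concerns primary open-angle glaucoma only.
- *That the Cycle 1 column can hold no data from patients given a second implant.* Protocol 8.7 allows unscheduled examinations and SAP 16.4 uses all post-baseline assessments, so an unscheduled field could fall there. The statement holds for scheduled fields.
- *That the comparison is biased between treatments.* The primary eye is randomised and its fellow receives the other treatment (Protocol 5.4), so pre-existing defects are balanced in expectation. The problem is dilution and mislabelling.

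**Conclusion.** The point holds as a limited one. As written, SAP 11.3.3 pools defects that predate treatment with new ones and calls the result incidence, whereas SAP 11.3.7 restricts its ungraded findings to those absent at baseline. The resulting dilution cannot be fixed from the documents. Over the assumed ranges, a true ratio of 2 or 3 would display as 1.02 to 1.31, under the assumptions that old defects persist and that a new defect in an already abnormal eye is invisible. The second assumption applies only to a single any-abnormality row.

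The schedule point needs no assumed rates: with visits in window, patients given a second implant have 0 scheduled fields in Analysis Cycle 1, so the Cycle 1 and Cycle 2 percentages are not comparable.

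The primary efficacy analysis is untouched. The effect is confined to one descriptive safety table and is partly mitigated by the mean deviation analysis. It is still worth correcting, because the remedy is cheap.

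**What to change.** In SAP 11.3.3, replace the categorical summary with the number and percentage of eyes, by treatment and finding type, that have a finding post-baseline which was absent at baseline.

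- **Baseline:** use the SAP 11.0 definition (the most recent non-missing field before SLT). Requiring absence on both pre-treatment fields is less suitable, because Protocol Table 2 allows the first to be done up to 10 months before Screening, and no rule covers two pre-treatment fields that disagree.
- **Timepoints:** Week 24, Week 52/Exit and overall.
- **Denominator:** at each visit, eyes with a baseline field and a field at that visit; for the overall row, eyes with a baseline field and at least one post-baseline field.
- **Cycle convention:** state that this by-visit display is an exception to the by-cycle presentation of SAP 11.0. If the cycle split is kept, restrict each cycle's denominator to eyes with a field in that cycle.

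The cost is SAP wording and programming. No new examinations are needed, since the schedule already includes a field during washout or at Baseline and the eCRF records findings by type. The matching table specification should be updated at the same time.

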### 11.3.4 Macroscopic Conjunctival Hyperemia

Severity assessment of hyperemia of both eyes is performed at Screening, Baseline, during Analysis Cycle 1 and during Analysis Cycle 2 for all patients and during Analysis Cycle 3. Conjunctival hyperemia severity in each eye is assessed as 0 (None), +0.5 (Trace), +1 (Mild), +2 (Moderate), +3 (Severe) or 'Not Evaluable'. These data will be summarized by eye using the worst severity of hyperemia observed by study period.

In addition, worst severity grade increase greater than 1 (worsening, i.e, a change from 0 to 2 and above, from 0.5 to 2 and above, or from 1 to 3 and above) in hyperemia from baseline will also be summarized for each eye by study period. If the worst severity grade during a period is less severe compared to baseline, it will be considered as 'no increase'.

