1.2.3 Clinical Studies with Bimatoprost SR

Study 192024-041D was a phase 1/2 paired-eye comparison study evaluating the safety and efficacy of 4 dose strengths of Bimatoprost SR (6, 10, 15, or 20 µg [2 x10 µg implants]), as single or repeat administrations in 1 eye (study eye), versus the use of topical LUMIGAN 0.03% once daily in the contralateral eye (nonstudy eye). The objective of this study was to evaluate the safety and IOP-lowering efficacy of Bimatoprost SR in patients with OAG.

A total of 109 patients received at least a single administration of Bimatoprost SR, and 24 patients received a repeat administration of Bimatoprost SR. A trend in dose response was observed across the 4 dose strengths that were tested.

Data suggest that the implant may provide topical prostaglandin analog-like efficacy up to 3 to 4 months post-implantation in the majority of patients. Data following the second administration in the retreated patients showed similar IOP lowering efficacy to that observed following the first administration of Bimatoprost SR. In addition, efficacy was maintained longer than the expected 4-month duration in many patients in this completed study. By Month 6, most patients (68%) were still maintained on monotherapy with the initial Bimatoprost SR implant administered. Among all Generation 2 dose strengths, 40% of patients had not received rescue or a second Bimatoprost SR treatment by Month 12. At Month 24, 28% of patients had not received rescue or a second treatment.

Bimatoprost SR showed an acceptable safety profile with single and repeat administrations in study 192024-041D. Most adverse events were ocular, mild or moderate in severity, occurred within the first 2 days after Bimatoprost SR administration, and were considered related to the study drug administration procedure. There were no reports of serious study drug-related adverse events, and no new safety concerns were observed after the second treatment. Please refer to the Investigator's Brochure for details on reported safety findings.

Two identical global phase 3 studies (Completed study 192024-091 and ongoing study 192024-092) were initiated in late 2014. These studies are assessing the safety and efficacy of Bimatoprost SR in multicenter, randomized, masked, parallel-group comparison studies of 2 dose strengths of Bimatoprost SR (10 and 15 µg) to an active control (timolol maleate 0.5%).

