Patients will receive a 360° administration of SLT in 1 eye on Day 1, and administration of Bimatoprost SR in the contralateral eye on Day 4, with a repeat administration of Bimatoprost SR at Week 16. Stage 1 patients (who enrolled and reached the Week 32 visit prior to implementation of Amendment 2) received a third administration of Bimatoprost SR at Week 32. In order to mask the patient to the treatment assigned to each eye, on Day 1 a Sham SLT procedure will be performed in the eye to be administered Bimatoprost SR (hereafter refer to as the “Bimatoprost SR eye”). A Sham Bimatoprost SR administration will be performed in the eye that underwent SLT (hereafter referred to as the “SLT eye”) on each Bimatoprost SR administration visit (Day 4 and Week 16) (see [Table 1](#)).

4. Study Population and Entry Criteria

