8.4.3.2 Day 2 (Phone Call)

On the day after study treatment administration, the patient will be contacted by telephone to collect the following:

- Collection of adverse events
- Collection of concomitant medications and procedures

If the patient reports symptoms or findings of concern in the Day 2 phone call (including but not limited to photophobia, blurred vision, eye pain, vitreous floaters), the investigator must bring the patient in for ophthalmic examination

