8.4.3.4 Cycle 1: Day 2 (Cycle 1 Safety Visit)

The following procedures are performed on Cycle 1 Day 2:

- Collection of adverse events
- Collection of concomitant medications and procedures

- Vital signs (at rest \geq 5 minutes)

The following procedures should be performed in both eyes (procedures in bold should be done in the order shown):

- **Pre-Hour 0 examinations** (may perform in any order before Hour 0 IOP):
 - Macroscopic conjunctival hyperemia assessment (The examination may also include, [REDACTED].)
 - Best-corrected visual acuity
- **Intraocular pressure measurement at Hour 0**
- **Non-contact examination:** The following may be performed at any time after the pre-Hour 0 examinations (including prior to Hour 0 IOP):
 - Biomicroscopy (The examination may also include, [REDACTED].)

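### For visual acuity and macroscopic hyperemia, the worst-value tables set an eye first examined 1 day after its active treatment against one first examined 4 to 7 days after

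*SAP*

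**What the plan says.** **Treatment days.** Protocol Section 3 (Study Design) states: "Patients will receive a 360° administration of SLT in 1 eye on Day 1", with "administration of Bimatoprost SR in the contralateral eye on Day 4". Protocol Table 3 allows +3 days on the implant day, so the first implant falls on study Day 4 to Day 7. Each eye receives a sham when the other is treated.

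**After SLT.** Protocol 8.4.3.2 schedules a call: "On the day after study treatment administration, the patient will be contacted by telephone". Adverse events and concomitant treatments are collected, and a patient who reports symptoms of concern must be brought in. On the SLT day itself, Protocol 8.4.3.1 schedules slit-lamp biomicroscopy and a single IOP reading after the laser. Macroscopic hyperemia is not listed there, and Protocol 6.2 excludes acuity testing on treatment days.

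**After each implant.** Protocol 8.4.3.4 sets a clinic visit for the next day: "The following procedures are performed on Cycle 1 Day 2". It covers macroscopic hyperemia, acuity, IOP and biomicroscopy in both eyes. Sections 8.4.3.8 and 8.4.3.12 repeat this for Cycles 2 and 3.

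**Summary rule.** For acuity, SAP 11.3.2 says: "The greatest line change in best corrected visual acuity (BCVA) from baseline will be summarized for each eye", categorized by study period. For hyperemia, SAP 11.3.4 says: "These data will be summarized by eye using the worst severity of hyperemia observed by study period". It adds a count of eyes whose worst grade rose by more than 1, also by period. Neither section has a by-visit summary. SAP 11.0 starts both Analysis Cycle 1 and the whole-study period on the SLT date.

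**The concern.** A worst-value summary depends on when the eye was looked at as well as on what happened to it. Here the Bimatoprost SR eye is graded the day after its procedure, and the SLT eye is not graded on these two measures until several days after its laser. If the effects are short-lived, the rule may catch the acute finding in one eye and miss it in the other, although the analysis period nominally covers the days after SLT.

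The protocol gives some reason to think the first days matter. Section 1.2.3 reports that in the phase 1/2 study most adverse events "occurred within the first 2 days after Bimatoprost SR administration". SAP 11.1 tabulates ocular adverse events separately for this interval: "Ocular TEAEs that occur within two days from the Bim SR treatment or Bim SR sham". The acuity and hyperemia tables have no such split.

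Safety compared with SLT is part of the study objective (Protocol 2.1), and ocular safety is summarized by treated eye (Protocol 7.3.4). A reader of these two tables could take a difference in examination timing for a difference in tolerability. The same reader could not tell whether a reported hyperemia grade or line loss lasted a day or persisted from Week 4.

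**Working it through.** The plan states no figure to reproduce. The check is a count of days and visits, followed by an illustration on assumed rates.

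**1. First examination.** SLT is on Day 1. The implant is on Day 4 to Day 7, and the first acuity and hyperemia examination is one day later, on Day 5 to Day 8.
- Bimatoprost SR eye: (implant day + 1) − implant day = 1 day after active treatment.
- SLT eye: 5 − 1 = 4 days, up to 8 − 1 = 7 days after active treatment.

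**2. Scheduled examinations of these measures** (Protocol Tables 3 to 6).
- Two implants: Cycle 1 Day 2 and Weeks 4, 8, 12, 15 (5); Cycle 2 Day 2 and Weeks 20, 24, 28, 31 (5); Weeks 36, 40, 44, 47, 52 (5). Total 15.
- Three implants: one more Day 2 visit. Total 16.
- Examinations the day after that eye's active treatment: 2 of 15 or 3 of 16 for Bimatoprost SR; 0 for SLT.

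The number and calendar dates of scheduled examinations are equal in the two eyes. Only the timing relative to active treatment differs.

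**3. Illustration with one implant.** Assume a share p of eyes show a finding the day after either procedure, and a share q still show it at 4 to 7 days. Ignore sham and background findings. The Bimatoprost SR eye is then recorded at p and the SLT eye at q.
- p = 15%, q = 3%: 15% against 3%, a gap of 12 points with no true difference per procedure.
- p = 5%, q = 1%: 5% against 1%, a gap of 4 points.

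**4. Range with background.** Let b = 5% be the chance of a finding at any other visit, and r the share of SLT findings still present at the first examination. The Bimatoprost SR eye is recorded at 1 − (1 − b)(1 − p) and the SLT eye at 1 − (1 − b)(1 − pr).
- p = 10%, r = 50%: 14.5% against 9.75%, a gap of 4.75 points.
- p = 30%, r = 0: 33.5% against 5%, a gap of 28.5 points.
- r = 1 (nothing fades before the first examination): no gap.

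**5. Two implants.** With p = 15%, the Bimatoprost SR eye is recorded at 1 − 0.85² = 27.75%, against 3% in the SLT eye, a gap of 24.75 points. If the SLT eye also had a day-after examination, it would be recorded at 15%. So 15 − 3 = 12 points come from timing, and 27.75 − 15 = 12.75 points come from the second implant, which is real added exposure.

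**6. Weeks 4 to 52.** At Week 4 the eyes differ in time since first active treatment by 4 − 1 = 3 to 7 − 1 = 6 days, with both several weeks past it. A worst value over these visits largely removes the timing problem.

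**The case against.** The case for leaving the tables alone has several good parts.

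- **The sham balances part of the contrast.** The SLT eye is examined the day after each sham, which has the same preparation and differs from the implant by the absence of a needle (Protocol 5.9.1.1, 5.9.1.3). Redness from preparation should appear in both eyes, so 3% for the SLT eye is a floor. This stands and narrows the likely size.
- **Symptomatic patients are examined.** The Day 2 call must lead to an examination if symptoms of concern are reported, and SAP 16.4 uses all postbaseline assessments for safety evaluation. The gap is therefore in scheduled examinations only. A reader might infer that the SLT eye is never examined in this interval, but the documents do not say so.
- **Adverse events are already separated.** SAP 11.1 tabulates ocular events between SLT and the first implant, and events within and after two days of implant or sham. This helps, but it does not supply hyperemia grades or acuity lines.
- **The comparison is descriptive**, and any timing effect of this kind would count against the investigational product. Both are true, and both limit the importance.
- **Table shells are in a separate document** (SAP 4.0) and might include a by-visit display. The SAP text does not call for one here, though it does for endothelial cell density and corneal thickness (SAP 11.3.5, 11.3.6).

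Three stronger readings are tempting and not supported. One extends the point to the slit-lamp findings in SAP 11.3.7, but that examination is done after the laser on the SLT day. Another takes the two-implant gap as a measure of the artefact, although about half of it is added exposure. The third holds that the tables hide what matters for benefit-risk. The stated concern is corneal events with repeat administration (Protocol 1.3), and corneal events of interest, cell density and corneal thickness have their own summaries.

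**Conclusion.** The point holds for best-corrected visual acuity and macroscopic conjunctival hyperemia only. Scheduled day-after-treatment examinations number one per implant in the Bimatoprost SR eye and none in the SLT eye. With only a greatest or worst value per period, the contrast in Analysis Cycle 1 and over the whole study partly reflects timing, provided that findings after SLT fade within days. In Analysis Cycles 2 and 3 the SLT eye has no active treatment, so a difference arising the day after an implant there reflects a real difference in regimen.

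The size cannot be determined from the documents. The illustration of about 15% against 3% rests entirely on assumed rates and ignores sham and background findings. The phase 1/2 statement concerns adverse events after the implant, at several dose strengths; it does not show how fast hyperemia or acuity loss resolves after SLT. Nor does the SAP say why it splits adverse events at two days, so a reader who takes that as an admission of this problem is inferring it.

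The matter is minor: a descriptive safety contrast, with no effect on the IOP primary analysis.

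**What to change.** In SAP 11.3.2 and 11.3.4:

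1. Keep the overall worst-value tables as they are, so that acute findings after the implant stay in view. Replacing them with a comparison from Week 4 onward would move those findings out of the main display.
2. Add a panel giving the worst value by eye over Weeks 4 to 52, leaving out the Day 2 safety visits.
3. Add a separate panel for the Day 2 visit of each cycle.
4. Footnote that the SLT eye has no scheduled acuity or macroscopic hyperemia examination until 4 to 7 days after SLT.

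No new data are needed. The cost is SAP wording and one or two extra panels per table, and the reader must consult more than one panel to see procedural and sustained findings.
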